	Category 2 - Red* with skin breakdown (moderate-severe)	As above for Category 1 +/-vesicles/bullae/skin erosion +/- denudation of skin +/- skin infection

If a subject does not meet all the Inclusion/Exclusion criteria, and is excluded from the study, the reason(s) for exclusion will be documented on the Screening Log.

If a subject meets all the Inclusion/Exclusion criteria, the Investigator or study nurse will obtain and open the randomization envelope to determine which product group the subject has been assigned to. The study nurse will complete the following remaining screening activities:

- Record subject demographics.
- Obtain and record IAD history.
- Obtain and record information describing current medications and IAD treatment.
 - Oral or systemic medications prescribed by the subject's physician are allowed and will be noted on the appropriate CRF.

- Incontinence-related devices (such as urinary catheters, pads, diapers, etc.) are allowed and will be noted on the appropriate CRF.
- Use of moisture barrier, creams, ointments, pastes, or other topical medications in combination with the Cavilon Advanced Skin Protectant product for the management of IAD is **not** allowed.
- If subjects had prior barrier film products on their skin, use the Brava Adhesive Remover Wipe.
- Conduct pressure ulcer risk assessment using Braden Scale.
- Administer Quality of Life questionnaire.
- Perform skin cleansing:
 - Use 3M[™] Cavilon[™] No-Rinse Skin Cleanser (to be provided by 3M) or warm tap water and soft cloths.
 - Avoid rigorous scrubbing to minimize friction damage.
 - Record pain score assessment using Faces Pain Scale Visual Analog before and after cleansing for adults or the FLACC scale for pediatrics during the cleansing process.
- Conduct skin assessment:
 - Complete a skin assessment of the following six zones for its color, presence of lesions, and skin loss. Only subjects with denuded skin may be enrolled. The IAD score will be calculated electronically once results are entered into computer system using 3M's validated Skin Condition Assessment Tool (see Appendix A).
 - Zone 1: Includes the anus and 2 inches surrounding anal opening plus: for males score the scrotal sac and females the labia majora.
 - Zone 2: Crease between buttocks, above the anal opening and 2-3 inches below natural waistline
 - Zone 3: Left buttock starts above fold between thigh and buttock and extends upward to 2-3 inches below natural waistline

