 - Zone 4: Left Posterior and medial upper thighs
 - Zone 5: Right buttock starts above fold between thigh and buttock and extends upward to 2-3 inches below natural waistline
 - Zone 6: Right Posterior and medial upper thighs

The score for each of the six (6) body zones will then be combined to obtain a single IAD score for the subject.

• Take photographs:

- Position the subject appropriately in order to capture all affected body zones.
- Take photograph including a paper ruler in the picture.
- o Download photographs immediately to the EDC system.
- Biomedical Systems is an outside vendor who will QC the photographs for correcting the color quality.

11. Study Assessments

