19.1 Statistical Methods

19.1.1 Efficacy Analyses

The primary analysis will be the percent change from baseline to last visit in IAD scores. The IAD score at each time point will be estimated using the assessments at each time point. The percent change from baseline will be calculated at the last visit and compared between treatment groups using an analysis of variance with site, treatment, age group (infants vs adults) and interactions as factors in the model. Lack of significance (P<0.05) for the age group-by-treatment will be used as justification for pooling the age groups. If the interaction is significant, the age groups will be analyzed separately. If appropriate, non-parametric procedures (e.g. ranking the data prior to analysis) will be used.

The primary analysis will be done using an intent-to-treat (ITT) population, using all subjects who have at least one dose of their assigned product. For this analysis, dropouts will be considered censored at the time of dropping out. Because two primary endpoints are being tested, Hocherg's procedure will be used to determine statistical significance to preserve the Type I error rate of α =0.05.

A second analysis will be done using a per protocol (PP) set. This analysis will be done on those subjects who were compliant with therapy and completed all procedures. This dataset will be defined prior to database lock, and all reasons for exclusion will be documented.

Analytical methods will be defined in detail in the approved Statistical Analysis Plan (SAP).

Secondary efficacy endpoints in this study will include:

- Time to resolution of severe Category 2 IAD, defined as re-epithelialization of skin. The time to resolution will be tested using a Cox Proportional Hazards model, with treatment group as a fixed factor in the model, and center as a random factor in the model. Other important prognostic factors (e.g., age, type and intensity of incontinence, use of corticosteroids, diabetes, use of warfarin) will be identified and may be included as covariates in the model. Kaplan-Meier estimates of time to re-epithelialization will also be done.

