19.2 Sample Size Justification

From a pilot study, the standard deviation of the percent change from baseline was estimated at 70%. A sample size of 51 patients per treatment group has at least 80% power to detect a mean difference of 45% change from baseline. The hypotheses tested will be:

 $H_0: \mu_T = \mu_C = 0$ versus $H_A: \mu_T \neq \mu_C$, where the subscript T = the investigational product and C = Control, the paste product.

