

41. Nix D and Ermer-Seltun J: A review of perineal skin care protocols and skin barrier product use. *Ostomy/Wound Management*. 2004; 50: 59-67.

30. APPENDIX A – 3M Skin Condition Assessment Tool merged with Beeckman et al 2015 Consensus Document: IAD Severity Categorisation Tool

Parameter	Intensity	Weight Multiplier Mild Cases					Severe Cases					
	(Area Involved)				Case 1	Case 2	Case 3	Case 4	Case 5	Case 6	Case 7	Case 8
Epidermal loss depth and area involved	None	0										
	Partial (skin open, not w eekping) or Complete (skin open and w eeping)		30		0	0	0	0	1	2	3	4
	1-25%	1										
	26-50%	2										
	51-75%	3										
	76-100%	4										
Skin Color of Intact Skin and % area if not normal color	Skin color: normal	0	0									
	Skin color: pink or red		1		1	2	3	4	0	0	0	0
	1-25%	1										
	26-50%	2										
	51-75%	3										
	76-100%	4										
Total Score					1	2	3	4	30	60	90	120

3M Confidential Document Name: CLIN-PROT-ICH-US-05-202767 Clinical and Non-Clinical: CLIN-INDEX-3M-SPON-US-05-012990

TABLE 1 | IAD Severity Categorisation Tool

Clinical presentation	Severity of IAD	Signs**				
	No redness and skin intact (at risk)	Skin is normal as compared to rest of body (no signs of IAD)				
T	Category 1 - Red* but skin intact (mild)	Erythema +/-oedema				
	Category 2 - Red* with skin breakdown (moderate-severe)	As above for Category 1 +/-vesicles/bullae/skin erosion +/- denudation of skin +/- skin infection				

31. APPENDIX B - Instructions for Use of 3M[™] Cavilon[™] Advanced Skin Protectant

3M[™] Cavilon[™] Advanced Skin Protectant

Product Description:

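### The primary ANOVA of percent change in IAD score has no baseline IAD covariate, giving up some precision and protection against chance imbalance at no saving

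*Combined protocol and SAP*

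**What the plan says.** Section 19.1.1 defines the primary analysis: "The primary analysis will be the percent change from baseline to last visit in IAD scores". On the comparison it says: "The percent change from baseline will be calculated at the last visit and compared between treatment groups using an analysis of variance". The model is an "analysis of variance with site, treatment, age group (infants vs adults) and interactions as factors in the model". The synopsis gives the same model. The age group-by-treatment interaction decides whether the age groups are pooled, and ranking the data first is allowed where appropriate.

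The baseline score exists for every subject. Section 10 (Screening and Enrollment) says: "The IAD score will be calculated electronically once results are entered into computer system using 3M's validated Skin Condition Assessment Tool". It adds: "The score for each of the six (6) body zones will then be combined to obtain a single IAD score for the subject".

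No supplied text puts that score into the primary model. Prognostic covariates are mentioned only as an option for the secondary Cox model, and the baseline IAD score is not among the examples. The sensitivity analysis in Section 19.4 concerns dropouts. Section 6.1 describes 1:1 randomization and no stratification by baseline severity. Section 19.1.1 leaves detailed methods to an SAP, but nothing supplied adds a baseline term.

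**The concern.** Expressing the outcome as a percentage of baseline can look like adjustment for baseline, but it is not. In Appendix A each band of "Epidermal loss depth and area involved" carries 30 points, so the same physical change is a large percentage for a subject who starts low and a small one for a subject who starts high. Improvement stops at -100% for everyone, while the room to worsen depends on where the subject began. Percent change can therefore remain correlated with baseline within each arm.

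If it does, two things follow. The part of the variance that baseline explains stays in the error term and widens the confidence interval. And a chance difference in baseline severity between the arms passes into the treatment estimate. The study nurse who applies the product is not blinded (Section 6.2), so a visible severity imbalance would be an obvious challenge to a superiority claim. An adjustment chosen after seeing the data would answer it less convincingly than one fixed in advance.

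**Working it through.** **Inputs from the documents.** SD of percent change 70 points, difference 45 points, 51 per arm, and power stated as at least 80% (Section 19.2). The alternative is two-sided (Section 19.2). Final-analysis significance level 0.0483 (Section 19.3). Score bands of 30 points (Appendix A).

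**Input not in the documents.** The within-arm correlation r between percent change and baseline (raw or log). It is varied below.

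**1. The plan's own figure.** Standard error of the difference = 70 × sqrt(2/51) = 13.86. Noncentrality = 45 / 13.86 = 3.25. The two-sided noncentral t with 100 df gives power of 89.5% at alpha 0.05 and 89.2% at alpha 0.0483. The stated lower bound of 80% is met without any covariate. Like the plan's calculation, this is a plain two-group comparison that ignores site and age terms.

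**2. Why division does not remove baseline.** One 30-point band as a share of the baseline score:

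| Baseline score | One band |
|---|---|
| 30 | 100% |
| 60 | 50% |
| 120 | 25% |
| 240 | 12.5% |

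One zone scores at most 120 for epidermal loss, so 240 assumes that the zones are added; Section 10 says only that they are combined. Averaging six zones gives the same ratio: 5/40 = 12.5%.

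**3. Effect of adjustment.** Residual SD = 70 × sqrt(1 − r²). Power is by noncentral t at alpha 0.0483. Equivalent unadjusted size per arm = 51 / (1 − r²). The sign of r does not matter here.

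| Assumed r | Residual SD | SE of difference | Power | Equivalent n per arm |
|---|---|---|---|---|
| 0 | 70.0 | 13.9 | 89.2% | 51 |
| 0.1 | 69.6 | 13.8 | 89.5% | 51.5 |
| 0.2 | 68.6 | 13.6 | 90.4% | 53.1 |
| 0.3 | 66.8 | 13.2 | 91.8% | 56.0 |
| 0.4 | 64.2 | 12.7 | 93.7% | 60.7 |

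**4. Effect of chance imbalance on the unadjusted estimate.** One standard error of the baseline difference is sqrt(2/51) = 0.198 SD. Shift = r × 70 × imbalance in SD units.

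| Assumed r | Shift at 1 SE (0.198 SD) | Shift at 1.96 SE (0.39 SD) |
|---|---|---|
| 0 | 0 | 0 |
| 0.1 | 1.4 points | 2.7 points |
| 0.2 | 2.8 points | 5.4 points |
| 0.3 | 4.2 points | 8.2 points |
| 0.4 | 5.5 points | 10.9 points |

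Given a 1.96-SE imbalance, the type I error conditional on it is 6.3% at r = 0.2 and 7.9% at r = 0.3, against a nominal 5% (normal approximation). At a 1-SE imbalance it stays at 5.0% for both.

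**5. What r might be.** Illustrative simulations on a scale of 30-point steps, with assumed baseline distributions and healing patterns, gave correlations from about -0.6 to +0.7. New breakdown on small denominators pushes r negative; less complete healing of severe cases pushes it positive, and the two can cancel. Requiring an SD near 70 does not settle it: one set of assumptions gave about 0.1, another about -0.4 to -0.6.

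**The case against.** The strongest reply is that nothing is broken. In a randomized trial the unadjusted comparison keeps its type I error over all randomizations, and power is already about 89% against a stated 80%. The gain rests on a correlation that nobody outside the sponsor can see; near r = 0.1 it is negligible. The ranking option would also dampen the extreme percentages that arise from small denominators. All of this stands, and it limits the point to precision and robustness.

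It does not follow that the covariate should be left out. It costs one degree of freedom if r is near zero and helps if r is 0.2 or more. The reference to a later SAP is only a partial answer, because the primary model's factors are already listed and baseline is not among them.

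A reader might also infer more than the documents support:
- That chance imbalance is likely because sites are small. Overall imbalance depends mainly on 51 per arm.
- That baseline severity is the strongest available predictor. No document says so.
- That a particular power gain can be promised for this trial. Any such figure depends on the assumed r.

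**Conclusion.** The omission is clear from the text: the primary model has no baseline IAD term, although every subject has the score. The consequence is modest and of uncertain size. At the plan's SD of 70 and difference of 45, moving from r = 0 to r = 0.4 takes adjusted power from about 89% to 94%. Over that range a one-standard-error imbalance moves the unadjusted estimate by 0 to 6 points, at most about 0.4 of its standard error (5.5 / 13.9). These figures rest on an assumed r and on a two-group approximation without site or age terms.

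It would be tempting to conclude that the primary test is invalid, inflates the false-positive rate or is underpowered. The documents do not support this: error is raised only conditional on a large observed imbalance, and the stated power is met. This is a worthwhile improvement that should be made, and the trial's conclusion does not hang on it.

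**What to change.** - In the primary model, prespecify the baseline IAD score on the log scale as a covariate. Keep site, treatment, age group and the interactions already named, including the age group-by-treatment test that decides pooling. The log is defined wherever percent change is, since both need a baseline above zero.
- If the ranking option is used, enter ranked baseline as the covariate.
- As a supportive analysis, fit an ANCOVA of the last-visit IAD score on baseline with the same terms.
- Use the same covariate for the secondary analysis of percent change at each visit.
- If subject-level pilot data are available, estimate r from them, so that the expected gain is known before database lock.

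Cost: SAP wording and one degree of freedom. No new data, visits or subjects.

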Outcome Measures:	Primary Efficacy Endpoint:
	The primary endpoint is percent change in IAD scores from baseline to end of study. Secondary Endpoint(s): Secondary end points will include: Time to re-epithelialization of denuded skin (defined as healing), time to progress from a severe Category 2 IAD to a Category 1 IAD or lower, avoidance of complications such as secondary infections and pressure ulcers efficacy in subjects who switch from the comparative group to the Cavilon Advanced Skin Protectant group after failure on the comparative group; Pain score comparison between the two products; Patient Quality of Life change from baseline; Nursing time; and Incontinence product use and associated cost.

Study Population:	Inclusion/Exclusion Criteria:								
	Subjects may be enrolled into this study if the answers to all these questions are yes .								
	 Is the subject a full term newborn (37 weeks or greater gestational age) or older? Is the subject in a facility providing nursing care 24 hours per day? Does the subject have severe Category 2 Incontinence-Associated Dermatitis-red with skin breakdown (i.e. skin erosion and denudation or denudation of skin alone) Is the subject willing to have photographs taken of their skin exposed to incontinence and permit use of photographs in potential publication? Is the subject willing to release rights to 3M for the use of the photos? Is there a reasonable expectation that the subject will remain in a facility for at least 7 days following enrollment in the study? Has the subject, or their legally authorized representative, signed an Institutional Review Board-approved informed consent/assent document and authorized the use and disclosure of protected health information? 								
	Subjects are excluded from participation in this study if any of the answers to these following questions is yes.								
	1. If female, is the subject pregnant or breast feeding or has she given birth within the 3 weeks preceding the screening visit?								
	2. Does the subject have a known allergy to acrylates or cyanoacrylates?								
	3. Does the subject have a Stage III, IV, unstageable, suspected deep tissue injury pressure ulcer in the area where the skin is affected by incontinence?								
	4. Does the subject have a preexisting skin disease on the areas affected by incontinence that may make skin assessments for this study difficult?								

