In this study, we propose to test a new 510(k) cleared moisture barrier film. This novel technology will adhere to severely damaged (denuded) and intact moist or wet skin in order to provide protection from liquid feces and other irritating body fluids and create an environment where healing can occur. This protective film coating will be more comfortable for subjects during application and wear. In addition, this product is easily cleaned and does not require frequent removal, making it more clinician friendly than paste barriers.

3. Device Description and Regulatory Status

3M[™] Cavilon[™] Advanced Skin Protectant was an investigative product at the start of this study in the fall of 2015. 3M submitted a Premarket Notification (510k) application and received clearance by the FDA on August 23, 2016. The Sponsor contends that the product, and its use in the study, poses a non-significant risk to the participants, and intends to conduct the study under the cleared medical device requirements at 21 CFR §812.2(c). (Protocol versions 1-6 were covered under investigational device regulations at 21 CFR §812.2(b) and Protocol 7 are covered under cleared 510(k) device regulations at 21 CFR §812.2(c)). The device does not meet the requirements of a significant risk device since it is not an implant, not being used to support or sustain life, not being used for diagnosing, curing, mitigating, or treating disease, and does not present a potential for serious risk to health, safety, and welfare of a subject. The product is an acrylate polymer technology that utilizes cyanoacrylate(s) as a component of the formulation. This formulation is delivered from a non-stinging, rapid drying solvent. Upon application to the skin it forms a breathable, protective, transparent coating.

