5.1 Primary Objective

The primary objective of this study is to compare the safety and efficacy of the recently 510(k) cleared product (3M[™] Cavilon[™] Advanced Skin Protectant), and to determine superiority compared to a commercially available moisture barrier paste with 15% zinc oxide (ConvaTec Sensi-Care[®] Protective Barrier), in the management of severe Category 2 Incontinence-Associated Dermatitis (red skin with denudement present) from urinary and/or fecal incontinence. The primary endpoint is percent change from baseline to end of study in IAD scores. Healing in this study is defined as reepithelialization of denuded skin.

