6.3 Sample Size

102 eligible subjects will be enrolled in this study across approximately 13 centers, with 51 subjects being enrolled in each product group. it is expected that each center will enroll between 8 and 15 subjects. If it is determined that ineligible subjects were enrolled (e.g. without denudement at baseline or leaving the study prior to the first assessment day), additional subjects will be enrolled so that a total of 102 eligible subjects will be enrolled in the study.

Page 16 of 54 Status: Release Version: 7 Issue Date: 8/31/2016 12:19:02 PM

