6.4 Study Duration

In order to screen, enroll, and complete 102 evaluable subjects, an enrollment period of approximately 18-24 months is anticipated. Each adult subject may be followed for up to a maximum of 42 days or until the subject is discharged. Each pediatric subject may be followed for up to a maximum of 21 days or until the subject is discharged.

- 1. If the subject is discharged prior to 21 days, the subject will still have met the requirements for study completion.
- 2. Adult Subjects (>18years) can remain in the study for up to 21 days following enrollment receiving the Cavilon Advanced Skin Protectant or comparative product. All subjects will be discontinued at this point with the exception of the following 2 scenarios:
 - Subjects randomized to the comparative group, who fail to reach healing at the end of 21-day period with ongoing incontinence may be crossed over to the Cavilon Advanced Skin Protectant group and allowed to continue for up to an additional 21 days.
 - Subjects randomized to the Cavilon Advanced Skin Protectant group, who either re-epithelized or have a positive reduction in their IAD during the 21-day period, but remain hospitalized and continue to have incontinence, may continue to receive the Cavilon Advanced Skin Protectant product for up to an additional 21 days to evaluate prevention of IAD reoccurrence.
 - If a subject completely heals during the study, they may be discontinued at that time.
- 3. Pediatric Subjects Full term (37 weeks) to 18 years) can remain in the study for up to 21 days following enrollment receiving the Cavilon Advanced Skin Protectant product or comparative product. If the subject is discharged prior to 21 days, the subject will still have met the requirements for study completion.
 - Subjects randomized to the comparative group, who fail to improve (IAD) within 3 days of first application in the study may be crossed over to Cavilon Advanced Skin Protectant group and allowed to continue for up to an additional 21 days. The staff should cleanse the skin, complete skin assessments, and photographs prior to application of Cavilon Advanced Skin Protectant.
 - Subjects randomized to Cavilon Advanced Skin Protectant group, who fail to improve (IAD) within 3 days of first application in the study may be discontinued.

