7.1 Primary Efficacy Endpoint

The primary efficacy endpoint will be percent change in IAD score from baseline to end of subject participation. The effect of skin protectants on clinical re-epithelialization of denuded skin in subjects with containment or resolution of urinary and/or fecal incontinence, as well as in subjects with ongoing urinary and/or fecal incontinence, will be observed. Skin condition will be determined using

clinical assessment data collected by means of a validated IAD skin assessment tool, and photographs.

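### Section 19.1.1 applies Hochberg for two primary endpoints when only one is defined, which conflicts with the levels in 19.3; and 19.3 plans a sample size re-estimation without stating its rule

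*Combined protocol and SAP*

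**What the plan says.** **One primary endpoint.** The synopsis states: "The primary endpoint is percent change in IAD scores from baseline to end of study". Section 5.1 states: "The primary endpoint is percent change from baseline to end of study in IAD scores". Section 7.1 states: "The primary efficacy endpoint will be percent change in IAD score from baseline to end of subject participation". Section 19.2 powers the trial on this endpoint alone (SD 70 points, difference 45 points, 51 per arm, at least 80% power), with a two-sided alternative. Section 19.4 refers to the primary endpoint in the singular.

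**Two primary endpoints.** Section 19.1.1 describes only the percent-change ANOVA as primary. It then invokes Hochberg at an overall 0.05 "Because two primary endpoints are being tested", with no second endpoint named. Time to re-epithelialization is listed as secondary in the synopsis, 5.2 and 19.1.1, and is paired with pain in a separate Hochberg adjustment.

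**Dropouts.** On the primary analysis 19.1.1 adds: "For this analysis, dropouts will be considered censored at the time of dropping out".

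**Interim.** Section 19.3 plans one look at half enrollment, at 0.0056 under an O'Brien-Fleming label, and a final level of 0.0483. The interim data are also to be used to re-estimate the sample size on the basis of the primary analysis, with study personnel kept blinded to the results. Input, target power, minimum, cap and any adjusted final test are not given. Section 19.1.1 defers detailed methods to an approved SAP.

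**The concern.** Two sections give different success rules for the same endpoint. Under 19.3 a final p of 0.03 is a success. Under Hochberg with two endpoints at 0.05, both are significant if the larger p is at most 0.05; otherwise the smaller must be at most 0.025. An IAD p of 0.03 would then fail if the second endpoint failed. Anyone programming the analysis would have to choose between these rules, possibly with data in hand.

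The re-estimation raises a separate question. The 0.0483 level accounts for the interim look but not for a change in N. Whether the overall 5% holds then depends on what drives the change. The SD alone does almost no harm; the observed treatment effect can do some. The wording of 19.3 permits either.

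The censoring sentence belongs to time-to-event analysis. It does not tell the analyst what value a dropout contributes to an ANOVA of percent change at last visit.

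**Working it through.** **Inputs.** From 19.2: SD 70, difference 45, 51 per arm, two-sided. From 19.3: levels 0.0056 and 0.0483, look at half enrollment. Assumed: information fraction 0.5 unless stated; all re-estimation targets, caps and floors; a 30-point difference as a smaller alternative.

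**1. The plan's own figure.** The standard error is 70 × √(2/51) = 13.86, so the noncentrality is 45/13.86 = 3.246 with 100 df. Noncentral t power at 0.05 is 89.5%. The claim of at least 80% is correct.

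**2. Power under each success rule.** Applying Hochberg's stricter step to the final level gives 0.0483/2 = 0.02415; applying it to 0.05 gives 0.025.

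| Level | Power at 45 points | Power at 30 points |
|---|---|---|
| 0.0483 | 0.8925 | 0.5669 |
| 0.025 | 0.8325 | 0.4584 |
| 0.02415 | 0.8290 | 0.4530 |

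The chance that p falls where the rules can disagree is the difference between rows: 0.060 to 0.063 at 45 points and 0.108 to 0.114 at 30 points. These are upper bounds, because a second primary must also exist and fail.

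**3. The two-look levels with N fixed.** The critical values are 2.770 and 1.975, with correlation √0.5 between looks. The bivariate normal gives an overall type I error of 5.05% at half information, 5.09% at 0.45, 5.02% at 0.55 and 4.98% at 0.60. A final level of 0.0478 gives 5.00% at half information.

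**4. Re-estimation from the observed effect.** Let z be the interim statistic, c = 1.975, and k the ratio of second-stage to first-stage size, so total N is multiplied by (1+k)/2.

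- Conditional power on the observed effect: Φ(|z|√k − (c√(1+k) − |z|)/√k).
- Null probability of upper-tail rejection given z: 1 − Φ((c√(1+k) − z)/√k), plus the matching lower tail.
- Rule assumed: raise k to reach 80% conditional power, never reduce N, and increase only if conditional power at the planned N is at least the floor.

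Integrating over z, with rejection at the interim if |z| ≥ 2.770 and the ordinary final test at 0.0483:

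| Floor | Cap 1.5× | Cap 2× | Cap 3× |
|---|---|---|---|
| none | 5.7% | 6.1% | 6.5% |
| 5% | 5.3% | 5.3% | 5.4% |
| 10% | 5.1% | 5.2% | 5.2% |
| 20% | 5.0% | 5.0% | 5.0% |

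A final test with pre-specified stage weights gives 5.05% under every one of these rules, the same as with N fixed. If the no-floor rule may also shrink the second stage, to a quarter of the first, the three figures become 6.7, 7.1 and 7.5%. A stated minimum therefore matters.

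**5. Re-estimation from the SD only.** Simulation used 2 million null trials per setting, 26 per arm at the interim, the 45-point difference fixed, minimum 51 and cap 102 per arm, target power 80 or 90%, blinded or unblinded SD, and true SD 60 to 100. Type I error was 5.1 to 5.3%, against 5.1% with no re-estimation.

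**6. What target power does to N.** At level 0.0483 and SD 70, 80% power needs 40 per arm and 90% needs 53. With an 80% target, 50 per arm suffice at SD 79 and 52 are needed at SD 80. N therefore starts to rise above 51 only at about SD 80, and power with 51 per arm at SD 79 is about 81%.

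**The case against.** **The Hochberg sentence is probably a leftover.** Every definition of the primary endpoint is singular, and with one endpoint 19.3 governs. This is the natural reading, and it makes the practical effect small. It does not remove the contradiction in the current text. Nor is it certain: 19.4 lists time to first healing among critical efficacy data, and 7.1, under the primary endpoint heading, says re-epithelialization will be observed. Intent should be confirmed before anything is deleted.

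**The SAP may supply the rule.** Section 19.1.1 does defer to one. The supplied text contains no re-estimation rule, so the claim is limited to that. A deferral also cannot settle a conflict between two sections that are already written.

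**The harm from re-estimation is small under most rules.** This stands. Only effect-based rules without a conditional-power floor give clear inflation among the increase-only rules examined, and nothing in the documents points to such a rule.

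**The censoring sentence should not simply go.** It is the only statement in 19.1.1 on dropouts in the primary analysis. It needs replacing.

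**Readings to avoid.** A reader might infer that 0.0483 is an unadjusted level. It is set alongside the O'Brien-Fleming interim level and lacks only an adjustment for re-estimation. A reader might infer that the trial is underpowered if Hochberg applies. Power is still 83%. A reader might infer that the plan inflates type I error. With the rule unstated, the documents show only that control is not assured.

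**Conclusion.** The concern holds in two limited parts and should be fixed.

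First, the primary success rule contradicts itself between 19.1.1 and 19.3. The consequence is bounded at about 6% of trials at 45 points and 11% at 30, and arises only if a second primary exists and fails. The stated power survives either way. This part alone is a wording correction.

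Second, the re-estimation has no stated rule in the supplied text. This is the weightier part, because overall error control depends on a choice left open: about 5.0 to 5.4% under SD-only rules or floored effect-based rules, and 5.7 to 6.5% under effect-based rules with no floor. These figures assume half information, increase-only rules, an 80% conditional-power target for the effect-based rules and the caps shown.

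The slight overspend of the 0.0056/0.0483 pair (5.05% at half information) is minor.

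**What to change.** **Confirm intent.** Establish whether a second primary endpoint was meant.

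- If not, delete the Hochberg sentence in 19.1.1, state percent change in IAD score as the single primary endpoint judged at the 19.3 levels, and keep Hochberg for the two secondaries (pain and time to re-epithelialization).
- If so, name it in 5.1, 7.1 and 19.1.1, and say how Hochberg applies at each look.

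**Replace the censoring sentence.** For the primary ANOVA, subjects who drop out contribute their last post-baseline IAD assessment, in line with the last-visit definition in 19.1.1. Keep the 19.4 sensitivity analysis that counts dropouts as worsening.

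**State the re-estimation rule in 19.3, if the interim has not taken place.** Use the SD only, with the 45-point difference fixed, no reduction below 102, a stated target power, a stated cap and the ordinary final test. If the observed effect is to be used, adopt a final test with pre-specified stage weights (Cui-Hung-Wang) and state the conditional-power range and cap. A final level of 0.0478 is optional and costs about 0.1 point of power (0.8925 to 0.8916).

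**Costs.** An SD-only rule cannot react to an effect smaller than planned. An 80% target lets power fall from 89% at SD 70 to about 81% at SD 79 before N grows; a 90% target avoids this but already asks for 53 per arm at SD 70. The weighted test loses slight efficiency. The rest is wording.

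**Timing.** Section 3 says the product "was an investigative product at the start of this study in the fall of 2015", and 6.4 says "an enrollment period of approximately 18-24 months is anticipated". With even accrual (assumed), half enrollment falls 18/2 = 9 to 24/2 = 12 months in, close to this version's issue date of 8/31/2016. If the interim has already been run, limit the re-estimation change to what can still be pre-specified. The Hochberg sentence can still be removed as a documented correction.
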